SYNOPSIS

PROTOCOL AnticipUSC – N°ICO 2016-A-04

A) Clinical Trial Identification

TITLE OF THE TRIAL: *Multicenter, open-label, randomized study comparing early postoperative prophylactic non-invasive ventilation in the intensive care unit versus standard postoperative follow-up in patients at high risk of postoperative pulmonary complications according to the preoperative ARISCAT score, undergoing surgery under general or regional anesthesia (ANTICIPUSC)*

SHORT TITLE: ANTICIPUSC

COORDINATOR: [name] [name]

ESTIMATED NUMBER OF CENTERS: 3

NUMBER OF PATIENTS: 266

B) Sponsor Identification

NAME OF THE ORGANIZATION: ICO, DRCI-Cellule de Promotion

CONTACT PERSON: MME [name]

[contact]

[contact]

C) General Information About the Trial

Indication:

This study will focus on a selected population at high risk of postoperative pulmonary complications (PPC) according to the ARISCAT score, among all surgical patients in the participating centers, whether undergoing surgery under General Anesthesia (GA) or Regional Anesthesia (RA), who may benefit from preventive postoperative management.

Primary objective:

The primary objective of the study is to compare the effectiveness of a preventive postoperative management strategy using non-invasive ventilation (NIV) in the intensive care unit versus standard care, on the incidence of acute respiratory failure within 7 postoperative days during hospitalization, in patients at high risk according to the ARISCAT score.

Secondary objectives:

- The safety and tolerability of the strategy under study
- The cause of acute respiratory failure (arf) among the different postoperative pulmonary complications (ppc)
- Mortality during hospitalization for surgery, up to a maximum of 7 days
- Any effect on patient reintubation (cause and timing)
- Any effect on the length of stay in the icu/intensive care unit and on invasive or non-invasive mechanical ventilation
- Any effect on the incidence of healthcare-associated infections, defined according to the centers for disease control (cdc) criteria.

Inclusion criteria:

1. Patient aged 18 years or older
2. Patient scheduled for elective surgery or considered semi-urgent (pre-anesthesia consultation < 48 hours before the surgical procedure), under General Anesthesia (GA) or Regional Anesthesia (RA)
3. Patient with an ARISCAT score greater than or equal to 45 (high risk of PPC)
4. Written informed consent signed by the patient

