5. Patient affiliated with a social security system

Exclusion criteria:

1. Minors, pregnant or breastfeeding women
2. Obstetric procedures
3. Surgeries under Local Anesthesia (LA) or peripheral nerve block
4. Procedures performed outside an interventional room (e.g., operating theater or interventional radiology)
5. Procedures related to previous surgical complications
6. Patients reoperated during follow-up (no double inclusion for the second surgery)
7. Organ transplantation
8. Patients already intubated preoperatively
9. Outpatient surgery
10. Refusal to participate or inability to provide informed consent
11. Persons deprived of liberty or adults under guardianship
12. Participation in another interventional study.

Primary endpoint:

Occurrence of acute respiratory failure (ARF) within 7 postoperative days during hospitalization, validated by the blinded adjudication committee with respect to the randomization arm.

Secondary endpoints:

Assessment of the safety and tolerability of the strategy under study:

- Discomfort or intolerance to NIV, defined as the inability to achieve the target of 6 to 8 hours per day due to premature termination of sessions caused by intolerance, despite proper implementation of NIV, including excessive leaks when these are the reason for stopping sessions
- Skin lesions at contact points between the interface and the patient's skin
- Anastomotic suture dehiscence (digestive or bronchial) when caused by a total pressure (PEEP + IPAP) > 20 cmH₂O
- Gastric distension defined as aeric distension of the gastric air pocket evidenced by imaging or gastric tube aspiration
- Occurrence of aspiration of secretions or vomit whose evacuation was hindered by the NIV mask

Any ARF must lead to investigation of its etiology using appropriate examinations:

Infectious pneumonia defined by a Modified Clinical Pulmonary Infection Score (CPIS) > 6, with microbiological thresholds of culture concentrations >10³ CFU/ml for a protected distal sample, >10⁴ CFU/ml for bronchoalveolar lavage, and >10⁶ CFU/ml for tracheal aspiration

The Modified Clinical Pulmonary Infection Score (modified CPIS)

CPIS Points	0	1	2
Tracheal secretions	Rare	Abundant	Abundant + purulent
Chest X-ray infiltrates	No infiltrate	Diffused	Localized
Temperature, °C	≥36.5 and ≤38.4	≥38.5. and ≤38.9	≥39 or ≤36.4
Leukocytes count, per mm ³	≥4,000 and ≤11,000	<4,000 or >11,000	<4,000 or >11,000 + band forms ≥500

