
- Death from any cause during hospitalization for surgery

Assessment of an effect on patient reintubation:

- Reintubation due to respiratory failure (ARF)
- Reintubation due to non-respiratory failure, excluding reintubations specifically for a new surgical or interventional radiology procedure
- Time to reintubation to assess delayed reintubation (characterized by a non-significant difference in reintubation rate between groups but a longer delay in the NIV group)

Assessment of an effect on length of stay in ICU and duration of invasive or non-invasive mechanical ventilation:

- Number of days of invasive mechanical ventilation (intubated or tracheostomized) during hospitalization for surgery, including episodes of reintubation
- Number of days of non-invasive mechanical ventilation (NIV) during hospitalization for surgery, including prophylactic and therapeutic NIV.

**Assessment of an effect on the incidence of healthcare-associated infections, defined according to
Centers for Disease Control (CDC) criteria:**

- Infectious pneumonia: see secondary endpoint criteria
- Urinary tract infection: fever $> 38^{\circ}\text{C}$ and urine culture showing no more than two microbial species, at least one with a concentration $> 10^5 \text{ CFU/ml}$, in a patient with no other obvious source of infection
- Catheter-related infection: fever $> 38^{\circ}\text{C}$, positive catheter culture or sample, and resolution of fever within 48 hours after catheter removal without antibiotic change and no other identified source of infection
- Bacteremia: fever $> 38^{\circ}\text{C}$ and at least one positive blood culture (two or more if coagulase-negative staphylococcus)
- Surgical site infection

Data collection is performed prospectively throughout the first 7 days of hospitalization for surgery.

D) Description of Investigational Medicinal Products

MEDICAMENTS :

Name of the Medicinal Product (INN)	Brand Name	Pharmaceutical Form	Route of Administration	Dosage per Administration
Medical Liquid Oxygen	N/A	Gas	N/A	

Therapeutic regimen:

The ventilatory mode used will be an assisted mode (PSV or BiPAP), as these have shown a stronger (86) and more sustained effect (29) than CPAP alone.

The interface—nasal mask, face mask, or helmet—is chosen according to the unit's usual practice.

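### Blinded adjudication is stated only for the occurrence of ARF; no blinded assessor is named for the cause of ARF or the reason for reintubation, in an open-label trial

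*Combined protocol and SAP*

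**What the plan says.** The title in section A describes a "Multicenter, open-label, randomized study". Under Primary endpoint in section C, the occurrence of ARF within 7 postoperative days is "validated by the blinded adjudication committee with respect to the randomization arm". The adjudication committee is mentioned nowhere else, and its working procedure is not described.

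Three groups of secondary endpoints attach a cause or a diagnosis to an event:

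- **Cause of ARF.** "Any ARF must lead to investigation of its etiology using appropriate examinations". A list of causes follows, most with a definition. No assessor is named, and nothing says whether one cause or several may be recorded.
- **Reason for reintubation.** One category is reintubation due to ARF. The other is "Reintubation due to non-respiratory failure, excluding reintubations specifically for a new surgical or interventional radiology procedure". There are no attribution criteria and no named assessor.
- **Pneumonia.** "Infectious pneumonia defined by a Modified Clinical Pulmonary Infection Score (CPIS) > 6", together with culture thresholds by type of sample. The list of healthcare-associated infections reuses this definition ("Infectious pneumonia: see secondary endpoint criteria").

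In section E, the paragraph on selection of patients for analysis says that available endpoints are analysed from the case report forms. Reintubation is item (c) in section E's list of secondary comparisons between arms. Cause of ARF is a stated secondary objective but is not in that list.

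**The concern.** When the arm is known, an event can be moved from one cause to another while the number of events stays the same. A belief that prophylactic NIV prevents respiratory failure could make a borderline reintubation in the NIV arm look non-respiratory, or make the same case in the control arm look respiratory. The plan guards against this for whether ARF occurred. It states no such guard for why ARF occurred or why the patient was reintubated.

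At stake are the ARF-related and non-respiratory reintubation rates and the distribution of ARF causes by arm. The new-procedure exclusion adds a further route, because a reintubation classed that way leaves both counts.

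**Working it through.** **1. Do the categories overlap?** The ARF causes and the reintubation categories, both under Secondary endpoints in section C, can be set side by side:

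| Clinical picture | In the list of ARF causes | If reintubated, could be coded as |
|---|---|---|
| Glasgow score of 12 or less | Yes, under upper airway obstruction | ARF or non-respiratory |
| Other surgical complication | Yes, as an example of other etiology | ARF, non-respiratory, or excluded as a new procedure |
| Aspiration | Yes, twice: under upper airway obstruction and as aspiration pneumonia | ARF, with the cause uncertain |

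No rule in the plan decides between the options in the last column.

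**2. How much of pneumonia is judgement?** The modified CPIS has six items of up to 2 points, so a maximum of 6 × 2 = 12. Secretions and X-ray infiltrates depend on the reader and carry 2 + 2 = 4 points. The oxygenation item (2 points) also requires a view on whether ARDS is present. Temperature, leukocytes and microbiology are measured. Pneumonia is therefore much better protected than reason for reintubation.

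**3. How many ARF cases should the committee already validate?** The plan's total is 242 + 24 = 266, or 133 per arm. (The 121 per arm behind it reproduces at 80% power, not the stated 90%. That is a separate matter, and the planned 266 is used here.)

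- At the planned rates of 30% and 15%: 133 × 0.30 + 133 × 0.15 = 39.9 + 19.95 ≈ 60.
- At the upper control rate of 50%, halved to 25%: 66.5 + 33.25 ≈ 100.

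These are expected ARF cases. Suspected cases that the committee reviews and rejects would add to them.

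**4. How far could relabelling move the result?** The documents give no reintubation rate, so the inputs here are assumptions. Let a proportion R of each arm be reintubated, a fraction f of these for ARF, with no true effect of NIV. If a fraction m of the ARF reintubations in the NIV arm is labelled non-respiratory, then:

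- patients moved = 133 × R × f × m
- apparent risk ratio = R·f·(1 − m) / (R·f) = 1 − m

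| R | f | ARF reintubations per arm | Moved at m = 10% | m = 20% | m = 30% |
|---|---|---|---|---|---|
| 5% | 70% | 4.7 | 0.5 | 0.9 | 1.4 |
| 10% | 70% | 9.3 | 0.9 | 1.9 | 2.8 |
| 10% | 100% | 13.3 | 1.3 | 2.7 | 4.0 |
| 15% | 70% | 14.0 | 1.4 | 2.8 | 4.2 |
| Apparent risk ratio | | | 0.90 | 0.80 | 0.70 |

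If the relabelling is in the control arm instead, the ratio is 1/(1 − m): 1.11, 1.25 and 1.43. A shift of roughly 0.5 to 4 patients therefore moves the point estimate by 10–30% towards NIV, or by 11–43% against it.

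Such a shift would not make a null result significant. With 9 to 11 versus 13 events out of 133, Fisher's exact p is about 0.5 to 0.8.

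**5. What happens to total reintubation?** Moving a case between ARF and non-respiratory leaves the total unchanged. Moving a case to the new-procedure exclusion removes it. If a fraction x of one arm's reintubations is moved in this way, the total for that arm is multiplied by 1 − x.

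**The case against.** A reader might infer that unblinded site staff make these attributions. The documents do not say so. They name no assessor, and analysis from case report forms does not settle who codes a cause. The committee may already cover these items in a procedure that the plan does not describe. This stands, and the point is limited to the absence of a stated blinded assessor.

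A reader might also conclude that all these endpoints are free judgement. That is too strong. Pneumonia has a numeric rule and culture thresholds. Pulmonary embolism needs contrast imaging or confirmed venous thrombosis, and effusion and atelectasis have imaging criteria. Overlap between causes remains, as does the lack of any criterion for the reason for reintubation.

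Reintubation for ARF is also partly anchored. A patient coded as a non-respiratory reintubation may carry a committee-validated ARF, and the conflict would then be visible. But validating that ARF occurred does not establish that it was the reason for the reintubation, and the plan does not say how such a conflict is resolved.

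The illustration rests on assumed rates and involves few patients. That is correct: it shows that the estimate is sensitive, not that bias will occur.

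**Conclusion.** The point holds as a gap in protection for two secondary classifications: the cause of ARF and the split of reintubations into ARF, non-respiratory and excluded new-procedure cases. The open-label design, the overlapping categories and the lack of a stated blinded assessor leave those results open to classification bias.

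The size depends on a reintubation rate that the documents do not give. Under the assumed 5–15%, a handful of relabelled patients in one arm is enough for a spurious relative change of 10–30% or more in ARF-related reintubation, without statistical significance.

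The documents do not support reading this as a threat to the primary result, because ARF occurrence is validated blind. Nor do they support reading it as a bias in reintubation overall, because the total can change only through the new-procedure exclusion. Pneumonia is a minor part of the point.

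**What to change.** Extend the written remit of the existing blinded committee:

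- On each ARF file it validates, the committee also codes the cause or causes of ARF and the reason for any reintubation (ARF, non-respiratory, or new procedure).
- All other reintubation files go to the committee as well, including those classed as new-procedure, so that the exclusion is also decided blind.
- The analysis uses the committee's codes.
- Committee coding of pneumonia is optional and can be limited to the reader-dependent CPIS items.

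If a committee procedure already covers this, one sentence in the plan is enough.

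The cost is extra coding on about 60 expected ARF files (about 100 at the upper control rate), plus the reintubation files without ARF, whose number the documents do not give. No extra patients or tests are needed. The change protects how a reintubation is labelled. It does not correct the decision to reintubate, which is still made with the arm known, and the report should say so.

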Statistical analyses will be performed using R software and IBM SPSS.

A total of 266 patients are planned for inclusion, divided into two balanced groups.

DESCRIPTION OF PLANNED STATISTICAL METHODS:

Research Protocol

Patients will be analyzed on an intention-to-treat basis and then per-protocol.

Intention-to-treat analysis: all patients included in the study for whom outcome data are available will be considered in the analysis according to their randomization group. No imputation method will be used in case of missing data.

If organizational constraints prevent the patient from receiving prophylactic NIV (despite inclusion in the corresponding intervention arm), the patient will remain in their randomization arm for the entire study duration, and their data will be analyzed on an intention-to-treat basis.

Per-protocol analysis excludes patients for whom the initial protocol was not fully adhered to. Only patients who followed the protocol will be considered in the analyses, within the arm to which they were originally randomized.

The analysis will focus on the primary endpoint to determine whether randomization to the "PPC prevention strategy" arm leads to a reduction in PPC frequency compared to the control group. Effect size and number needed to treat will be calculated.

Similarly, for secondary endpoints, significant differences between the two groups will be sought in terms of:

- a) Safety and tolerability of the strategy under study (see safety assessment parameters)
- b) Mortality during hospitalization
- c) Patient reintubation
- d) Length of stay and duration of invasive or non-invasive mechanical ventilation

Description of the overall analysis method

The significance threshold is set at 0.05, and all tests will be two-sided. For qualitative variables, results will be reported as counts and percentages. For quantitative variables, results will be reported as means and standard deviations in case of normal distribution, and as medians with 25th and 75th percentiles in the absence of a Gaussian distribution. Normality of continuous variables will be assessed using the Kolmogorov-Smirnov test.

A simple descriptive analysis will be performed on the entire study population and by subgroups. This description will include sociodemographic data, medical history, ongoing treatments, etc.

A qualitative and quantitative analysis of missing data will be performed. No imputation of missing data is planned for the endpoints.

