Study of Associations (Qualitative and/or Quantitative Variables):

For each parameter of interest, a bivariate analysis will be performed, possibly complemented by a multivariate analysis adapted to the outcome variable to explore potential associations.

For bivariate analyses, the use of parametric or non-parametric tests will depend on sample size and/or variable distribution. The significance threshold is set at 0.05, and all tests will be two-sided.

The statistical test used will be Pearson's Chi-square test (or Fisher's exact test) for qualitative variables. For quantitative variables, the statistical tests used will be ANOVA or the non-parametric Kruskal-Wallis test.

The association between each presumed risk factor and the parameter of interest will be estimated using the relative risk (RR) and its 95% confidence interval.

A multivariate logistic regression analysis will estimate the adjusted RR and its 95% confidence interval for each retained factor (conservative threshold of 0.20 in univariate analysis).

Early Mortality:

Overall survival is defined as the time between the date of operating room discharge and the date of death if the patient dies within 7 days, or the end of study follow-up at Day 7. The Kaplan-Meier method will be used to estimate survival rates and plot survival curves. The Log-Rank test will be used to compare survival curves. Event-free survival is defined as the time between operating room discharge and the date of occurrence of the event (PPC) or the date of last follow-up if censored.

A semi-parametric Cox proportional hazards regression model will estimate for each variable the crude association (Hazard Ratio, HR) between the factor studied and death (bivariate analysis), then the adjusted HR in multivariate analysis.

The significance threshold for including other variables in the multivariate analysis will be 0.20. If several candidate variables are redundant, the most representative variable will be retained for the model.

Subgroup Analyses (Exploratory):

Subgroup analyses will address the occurrence of endpoints:

- According to patient characteristics at inclusion (medical history, ARISCAT score components, type of surgery, and planned anesthetic technique).
- The subgroup of patients receiving NIV as curative (under conditions noted at session start) will be compared to the group receiving NIV only prophylactically in terms of outcome at Day 7.

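### The plan's definition of delayed reintubation rests on a non-significant rate difference and cannot tell harmful delay from early prevention of reintubation

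*Combined protocol and SAP*

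**What the plan says.** The secondary objectives in section C include reintubation as "Any effect on patient reintubation (cause and timing"). In the secondary endpoints of section C, the timing part becomes "Time to reintubation to assess delayed reintubation", which is then explained in brackets as "characterized by a non-significant difference in reintubation rate between groups but a longer delay in the NIV group". The bracket gives no margin or confidence-interval criterion for the rates. It does not say whether the longer delay must be significant, when the clock starts, or which patients are compared.

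Section E supplies only general rules:

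- "for secondary endpoints, significant differences between the two groups will be sought in terms of" a list of items that includes reintubation.
- "The significance threshold is set at 0.05, and all tests will be two-sided".
- Under Study of Associations, rates are compared by "Pearson's Chi-square test (or Fisher's exact test) for qualitative variables". For quantitative variables, "the statistical tests used will be ANOVA or the non-parametric Kruskal-Wallis test".
- Kaplan-Meier and log-rank methods appear under Early Mortality. There, "Event-free survival is defined as the time between operating room discharge and the date of occurrence of the event (PPC"). Reintubation is not named as an event.

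**The concern.** The definition has two parts, and each is weak.

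First, it lets a non-significant test stand for similar reintubation rates. The trial is sized on acute respiratory failure (ARF), 30% versus 15%, not on reintubation. A non-significant result is likely even when NIV halves the reintubation rate.

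Second, the delay is most naturally compared among patients who were reintubated, a group formed after randomisation. Prophylactic NIV ends within 48 h at the latest (section D), and the plan hopes that it will prevent reintubation (Expected outcomes). If it does so mainly while it is being given, the reintubations left in the NIV arm are later ones. The average delay then lengthens although no patient was reintubated late because of NIV.

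Delayed reintubation would be read as a safety finding about the strategy. Under this definition, a protective effect could be reported as a harmful delay.

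**Working it through.** **Inputs from the plan.** 121 evaluable patients per arm; two-sided alpha 0.05; chi-square or Fisher test for rates; 7-day window; NIV for at most 48 h; expected relative reduction of about 50%. The plan gives no figure for reintubation rate, delay or the behaviour of the definition.

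**The plan's own figure.** For 30% versus 15% (mean 22.5%), n = [z(0.975)·√(2·0.225·0.775) + z(power)·√(0.30·0.70 + 0.15·0.85)]² / 0.15².

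- At 80% power: (1.960·0.5906 + 0.842·0.5809)² / 0.0225 = 120.5, so 121.
- At the stated 90%: (1.960·0.5906 + 1.282·0.5809)² / 0.0225 = 160.8, so 161.

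The 121 per arm therefore corresponds to 80% power. That is a separate matter for the sponsor to reconcile; 121 is used below as the planned size.

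**Power for reintubation (control rate assumed).** Power = Φ{[d√121 − 1.96·√(2p̄(1−p̄))] / √(p₁(1−p₁) + p₂(1−p₂))}, where d = p₁ − p₂ and p̄ is the mean rate.

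- 5% vs 2.5%: (0.275 − 0.527)/0.268 = −0.94, power 17% (exact chi-square 16%).
- 10% vs 5%: (0.550 − 0.730)/0.371 = −0.49, power 31%.
- 15% vs 7.5%: (0.825 − 0.876)/0.444 = −0.11, power 45% (exact 46%).

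With equal rates, the 95% CI half-width is 1.96·√(2p(1−p)/121), which is 5.5, 7.6 and 9.0 percentage points at 5%, 10% and 15%. Against rates of this size, such an interval cannot establish similarity.

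**How often the definition is met.** Simulation: 121 per arm, 7 days, 5,000 trials per cell (Monte Carlo standard error at most √(0.25/5000) = 0.7 points). Rates were compared at 0.05 by chi-square, or by Fisher when expected counts were below 5. Delay was compared among reintubated patients. Each cell shows the percentage of trials with a non-significant rate difference and (first figure) a numerically longer median delay under NIV, or (second figure) a delay significantly longer by a rank test. Three timing patterns were assumed: constant hazard; front-loaded (cumulative hazard proportional to √t); and exponential with mean 2.5 days, truncated at Day 7. 'Early ×0.5' and 'Early ×0.25' mean that hazard or risk is multiplied by that factor in the first 2 days only.

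| Control rate, timing | No effect | Halved throughout | Early ×0.5 | Early ×0.25 |
|---|---|---|---|---|
| 5%, constant | 48.1 / 1.8 | 43.3 / 0.9 | 59.9 / 3.5 | 64.1 / 4.3 |
| 5%, front-loaded | 47.8 / 1.7 | 43.6 / 0.9 | 63.0 / 3.9 | 70.3 / 6.5 |
| 5%, exponential | 48.2 / 1.5 | 43.9 / 1.1 | 62.5 / 3.9 | 71.1 / 5.7 |
| 10%, constant | 46.9 / 2.2 | 36.9 / 1.4 | 60.3 / 5.4 | 65.7 / 8.7 |
| 10%, front-loaded | 47.7 / 1.9 | 36.4 / 1.7 | 67.1 / 8.1 | 70.4 / 15.2 |
| 10%, exponential | 46.4 / 2.1 | 35.8 / 1.3 | 66.2 / 8.0 | 65.4 / 13.3 |
| 15%, constant | 46.6 / 2.3 | 30.5 / 2.0 | 64.0 / 7.2 | 70.4 / 14.9 |
| 15%, front-loaded | 46.4 / 2.4 | 30.7 / 1.6 | 69.6 / 10.9 | 67.6 / 21.9 |
| 15%, exponential | 47.9 / 2.3 | 26.9 / 1.3 | 66.2 / 9.0 | 60.5 / 19.1 |

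Repeat runs moved these by about a point, so the ranges quoted elsewhere are rounded outward. The non-significance condition alone is met in about 94–96% of trials with no effect and 54–89% with a true halving.

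**Comparison with a real delay.** If NIV shifts every reintubation by 1 day and does nothing else (constant or front-loaded timing), the definition is met in 58–73% of trials on the numerical reading and 3–26% on the significant one. Early-only benefit gives about 60–71% and 3–22%. The ranges overlap almost completely.

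**The case against.** The strongest reply is that 'longer' should be read as significantly longer. The bracket itself speaks of significance for the rate, and section E seeks significant differences for secondary endpoints at 0.05. This reading is permitted. It cuts the frequency under no effect from just under half to about 2%. A reader might infer that the definition often labels an ineffective strategy as delaying reintubation; the documents support that only if a numerical difference suffices, and they do not say so.

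A reader might also infer that any benefit makes the label more likely. It does not: a uniform halving gives 27–45% on the numerical reading, below the no-effect figure. Only benefit concentrated in the first 48 h raises it. The NIV schedule makes that shape plausible but does not establish it.

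The comparison among reintubated patients is also inferred. It is the natural reading, because ANOVA or Kruskal-Wallis needs a delay value for each patient and the survival methods are not extended to reintubation. Using all randomised patients would not rescue the definition. With mean time free of reintubation to Day 7 as the delay, numerically longer under NIV, it is met in about 46–49% of trials with no effect, 53–71% with a uniform halving and 63–73% with a true 1-day delay. There, longer time is simply what benefit looks like.

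Finally, the wording is a bracketed gloss on one secondary endpoint. No stopping rule or decision depends on it, reintubation is listed apart from the safety and tolerability items, and reintubation rates would be reported beside it. So the documents do not support a reading that the trial would declare NIV harmful on this basis. That limits the seriousness of the point but does not make the definition sound.

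**Conclusion.** The definition should not be used. Its first condition carries little information, because power for a halving is only about 16–46% at 121 per arm. Its second, read naturally, conditions on an event after randomisation.

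Two conclusions hold to different degrees. The risk of labelling an inert strategy as delaying applies only if 'longer' is numerical (about 46–49%, against about 2% if the delay must be significant). The inability to separate early prevention from harmful delay holds under both readings (about 60–71% or 3–22% under early-only benefit, close to the figures for a true 1-day delay).

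The control rates of 5–15%, the timing patterns and the effect shapes are all assumptions, since the plan gives none. The primary analysis is untouched. The change is worth making because the label bears on safety and the repair is cheap.

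**What to change.** Delete the bracketed definition. In the SAP:

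- Estimate the cumulative incidence of reintubation by arm, from operating room discharge to Day 7, in all randomised patients. Treat death without reintubation as a competing event. State how live discharge before Day 7 is handled, since data are collected during the hospital stay.
- Report the between-arm difference with its 95% CI at Day 7.
- To keep the timing objective, also report the difference at an earlier time such as 48 h, or the difference in restricted mean time free of reintubation.
- Describe times among reintubated patients without a test, and draw no conclusion of delayed reintubation from them.

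The cost is SAP wording and slightly more analysis on data already planned for collection. The trial gives up a yes/no label for delayed reintubation.
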